The orexin 1 receptor antagonist SB-334867 attenuated heroin SA in adult rats and diminished cue-induced, but not prime-induced, reinstatement of heroin-seeking behavior following extinction (Smith and Aston-Jones 2012). Also, orexin 2 receptor antagonists reduce heroin intake in long-access (12 h), but not short-access (2 h), SA paradigms (Schmeichel, Barbier et al. 2015). Orexin 1 receptor antagonists attenuate morphine withdrawal symptoms in rats (Azizi, Mirnajafi-Zadeh et al. 2010, Laorden, Ferenczi et al. 2012). Dual orexin antagonists seem to be particularly well suited to treating OUD. Han et al., (2020) reviewed all similar studies and found that there is evidence from multiple animal models of opioid addiction supporting the use of orexin 1 and 2 receptor antagonists to reduce addictive behaviors. Matzeau and Martin-Fardon et al., (2020) evaluated orexin 1 antagonist SB-334867 and TCSOX229 an orexin 2 receptor antagonist in rats with an oxycodone self-administration model showing that the orexin 1 receptor antagonist suppressed self-administration but not the orexin 2 receptor antagonist.

As a first step in evaluating the potential for use of the orexin 1 and 2 receptor antagonist lemborexant as an adjunctive treatment for opioid use disorder in patients in MAT with buprenorphine, we propose a phase 1b/2a drug-drug interaction study examining two doses of lemborexant as an add-on to buprenorphine-naloxone

with 18 participants (12 treated with lemborexant and 6 treated with placebo. The lemborexant group will have two lab sessions each; one with each dose of med). All participants will be currently stable in MAT treatment with buprenorphine and have symptoms of insomnia as measured by the Pittsburgh Sleep Quality Index. This is parallel groups ascending dose study.

Specific Aims:

Primary: Aim 1: To examine safety-tolerability and drug-drug interactions between lemborexant and buprenorphine-naloxone in participants with opioid use disorder and insomnia who are in MAT with buprenorphine-naloxone.

Secondary: Aim 2: To examine lemborexant for an early signal of efficacy (anticraving, anxiolysis, impulsivity, and reduced subjective withdrawal symptoms) in participants with opioid use disorder and insomnia who are in MAT with buprenorphine-naloxone.

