Study Hypotheses: 1. *Adjunctive lemborexant (compared to placebo) will not alter the PK of buprenorphine-naloxone significantly, nor will it alter the pharmacodynamic properties related to safety (e.g., ECG, pulse oximetry changes, capnography, significant increases in sedation and agitation).* **Secondary hypotheses:** 2. *Adjunctive lemborexant will reduce subjective opioid craving, anxiety, opioid withdrawal, and impulsivity).* **Exploratory hypotheses:** 3. *Adjunctive lemborexant will not affect central mu opioid receptors as measured by pupillometry, but will increase subjective sleep ratings and behavioral effects of lemborexant will be related to behavioral profile measures from the NIDA phenotyping battery.*

Brief description of the protocol: The overall goal of this project is to develop initial human data for lemborexant combined with buprenorphine-naloxone on safety (e.g., interactive effects on cardiovascular and respiratory function, and agitation and sedation) and efficacy (subjective craving and anxiety, opioid withdrawal and impulsivity) in opioid use disorder participants. The sample will be recruited from VCU MOTIVATE clinic and other treatment programs and consist of participants with opioid use disorder of at least moderate severity that have been stabilized on buprenorphine-naloxone sublingual film daily dose ranging from 8mg/2mg to 24mg/6mg or buprenorphine sublingual tablet dose ranging from 5.7mg/1.4mg to 17.1/4.3 once daily.

PRIMARY Endpoints:

1. Safety: Heart rate (HR), blood pressure (BP), respiration (pulse oximetry, end tidal CO₂ (EtCO₂), respiratory rate), agitation and sedation (Richmond Agitation Sedation Scale).
2. Buprenorphine PK: Plasma concentration-time profiles of buprenorphine and its metabolite norbuprenorphine
3. Lemborexant PK: Plasma concentration-time profiles of lemborexant and its major metabolite M10.

SECONDARY Endpoints:

1. Subjective effects on opioid craving, anxiety and lemborexant drug liking as measured by a visual analog scale (VAS), and Brief Substance craving scale (BSCS), and opioid withdrawal based on the Subjective Opioid Withdrawal Scale (SOWS).
2. Objective opioid withdrawal based on the Clinical Opioid Withdrawal Scale (COWS).
3. Impulsivity as measured by a delayed discounting task (DDT).

EXPLORATORY Endpoints:

1. Change in pupil size as an indicator of central nervous system mu-opioid pharmacological effects (Rollins, Feiner et al. 2014, measured by pupillometry.).

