2. Behavioral/clinical profiles correlated with treatment response generated from PhAB application.
3. Self-reported sleep measures.

SUBJECT SELECTION

Study Population

Subjects with a diagnosis of opioid use disorder who meet all of the inclusion and none of the exclusion criteria will be eligible for participation in this study.

N=18 (nine men and nine women) will be recruited from the VCU MOTIVATE or other outpatient treatment setting (note that we anticipate recruitment and randomization of up to 64 participants to complete 18 participants, see recruitment and enrollment figure at end of protocol).

INCLUSION/EXCLUSION CRITERIA

This study can fulfill its objectives only if appropriate subjects are enrolled. The following eligibility criteria are designed to select subjects for whom this clinical trial is considered appropriate. All relevant medical and non-medical conditions will be taken into consideration when deciding whether this protocol is suitable for a particular subject.

Inclusion Criteria:

- 1) Males and females between 18 - 65 years-of-age;
- 2) Understand the study procedures and provide written informed consent in English language;
- 3) Meet current DSM-5 criteria for opioid use disorder, of at least moderate severity, currently engaged in buprenorphine-naloxone treatment at a sublingual film daily dose ranging from 8mg/2mg to 24mg/6mg or buprenorphine sublingual tablet dose ranging from 5.7mg/1.4mg to 17.1/4.3 once daily;
- 4) Have a positive urine drug screen for buprenorphine during screening and on admission to the clinical research unit to document buprenorphine use;
- 5) Have a Pittsburgh Sleep Quality Index (PSQI) Total Score of 6 or higher.

Exclusion Criteria:

- 1) Contraindications for participation as determined by medical history and physical exam performed by study NP or study physician;
- 2) Pregnant or nursing women;
- 3) Baseline ECG with clinically significant abnormal conduction;
- 4) Uncontrolled serious psychiatric or major medical disorder, including COPD. Narcolepsy is also considered exclusionary;
- 5) Taking prescription or over-the counter drugs or dietary supplements known to significantly inhibit CYP3A4 (such as Clarithromycin, telithromycin, nefazodone, itraconazole, ketoconazole, atazanavir, darunavir, indinavir, lopinavir, nelfinavir, ritonavir, saquinavir, tipranavir), or CYP3A4 inducers (such as phenobarbital, phenytoin, rifampicin, St. John's Wort, and glucocorticoids);

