- 6) Prescribed medications for insomnia, or unable to discontinue over the counter drugs or dietary supplements used to treat insomnia on study days.
- 7) Current severe alcohol use disorder or current benzodiazepine use disorder
- 8) Current DSM-5 diagnosis of any psychoactive substance use disorder other than opioids, cocaine, marijuana, or nicotine, or mild or moderate alcohol use disorder. Diagnosis of mild to moderate use disorder for alcohol will not be considered exclusionary.
- 9) Any previous medically adverse reaction to opioids or lemborexant;
- 10) Significant current suicidal or homicidal ideation (C-SSRS "yes" answers on questions 4 or 5) or a history of suicide attempt within the past 6 months.
- 11) Subjects with Suicidal Behaviors Questionnaire-Revised score ≥ 8 at the screening visit.

12) Any other severe acute or chronic medical or psychiatric condition or laboratory abnormality that may increase the risk associated with study participation or investigational product administration or may interfere with the interpretation of study results and, in the judgment of the investigator, would make the subject inappropriate for entry into this study.

CONCURRENT MEDICATIONS

Concurrent Medications

All participants should be maintained on the same medications throughout the entire study period, as medically feasible, with no introduction of new chronic therapies. Non-CNS active medications which are known not to have any potential interaction with either buprenorphine or lemborexant would be allowed in this study. The following medications are prohibited during the study: Medications that may affect buprenorphine plasma levels; rifampin, phenobarbital, and phenytoin (CYP450 3A4 inducers) or such as ketoconazole, erythromycin, and saquinavir (enzyme inhibitors) that could affect the levels of parent drug or its active metabolites. Lemborexant is not thought to have any significant pharmacokinetic drug-drug interaction other than those that would inhibit CYP450 3A4, and thus would already be excluded based on the above criteria.

Prohibited

CNS active medications that in the opinion of the PI may affect interpretation of the study.

Medications which could potentially have clinically significant interactions with buprenorphine or lemborexant, notably drugs significantly inhibiting CYP3A.

STUDY TREATMENTS

Method of Assigning Subjects to Treatment Groups

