Patients will be randomly assigned to lemborexant or placebo treatment groups in a 2:1 ratio using a randomization scheme overseen by the unblinded research pharmacist, such that 18 patients complete both lemborexant dosing days.

Blinding

Due to the objectives of the study, the identity of test and control treatments will not be known to investigators, research staff, or patients. The following study procedures will be in place to ensure double-blind administration of study treatments:

- Access to the randomization code will be strictly controlled.
- Packaging and labeling of lemborexant and placebo will be identical to maintain the blind. Lemborexant concentrations will not be analyzed until the end of the study.
- The study blind will be broken on completion of the clinical study and after the study database has been locked.

During the study, the blind may be broken only in emergencies when knowledge of the patient's treatment group is necessary for further patient management. Unblinding will occur by the PI contacting the research pharmacy to break the blind in case of emergency.

Formulation of Test Product

Lemborexant 5 mg tablets (Eisai Pharmaceuticals) will be used for this study. To ensure blinding, tablets will be placed in gelatin capsules by the research pharmacist prior to administration.

Buprenorphine HCl/naloxone films will be used for this study, in unblinded fashion.

Formulation of Control Product: Gelatin placebo capsules identical to capsules that enclose the study drug will be used for placebo. Dextrose powder will be used as a filling in the capsules.

Packaging and Labeling

Each package of study drug will be labeled with the required FDA warning statement, the protocol number, a treatment number, the name of the study physician, and directions for patient use and storage.

Administration of Study Drug

Dosage/Dosage Regimen

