If subjects meet inclusion criteria, they will be admitted as research participants to the clinical research unit (CRU) for a total of up to 4 overnight stays across the two inpatient admission visits to maintain complete monitoring for adverse events. While in the hospital, subjects will undergo procedures as described below. Subjects will not be allowed to smoke cigarettes, as smoking is not allowed in the hospital or anywhere on the VCU campus. Subjects who are identified as current smokers will have the option to use a nicotine patch dosed based on the amount of daily cigarettes smoked. Subjects will not be allowed to leave the CRU nor receive visitors if they wish to remain in the study. Subjects who are unable to comply with these restrictions will be dropped from the study. Eligible subjects will be randomized to Group A –placebo only or Group B – lemborexant. Six subjects will be assigned to Group A (placebo) and 12 subjects will be assigned to Group B (active lemborexant).

Study Drug Dosage: 5 mg of lemborexant, and 10 mg of lemborexant, all subjects will receive a dose equivalent to their current prescribed dose of buprenorphine-naloxone sublingually as a film or tablet.

STUDY OUTCOME MEAURES

Primary outcome measures:

1. Safety: Heart rate (HR), blood pressure (BP), respiratory rate, agitation and sedation (Richmond Agitation-Sedation Scale), capnography (EtCO₂), and pulse oximetry during placebo administration will be compared to those same measures after lemborexant. Changes in safety measures induced by buprenorphine-naloxone dose along with lemborexant will be compared to those without lemborexant. Adverse event data will be compiled for lemborexant and placebo cohorts and presented as summary statistics.
2. Buprenorphine PK: Plasma concentration-time profiles of buprenorphine and its metabolite norbuprenorphine and after doses during the lemborexant placebo/administration (Day 0,1, 2) will be analyzed to obtain pharmacokinetic parameter estimates of buprenorphine (C_{max}, T_{max}, AUC, apparent t_{1/2}, CL/F for parent buprenorphine and metabolic (AUC) ratios for metabolites) by individual. In addition lemborexant and its main metabolite M10 will be determined after each dose of buprenorphine and compared with published lemborexant PK parameters.

Secondary Outcome Measures:

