All concomitant medication and concurrent therapies will be documented during screening, CRU study days, and Follow-Up days. Dose, route, unit frequency of administration, and indication for administration and dates of medication will be captured.

Clinical Opiate Withdrawal Scale (COWS) and Subjective Opiate Withdrawal Scale (SOWS)

These scales will be administered each study day during screening, admission to the CRU, and CARI or Motivate clinic study days to determine the presence of symptoms indicative of opiate withdrawal.

Demographics

Demographic information (date of birth, gender, race) will be recorded at screening.

Medical History

Relevant medical history, including history of current disease, other pertinent history, and information regarding underlying diseases will be recorded at screening.

Physical Examination

A complete physical examination will be performed by qualified staff (MD, DO, NP). New abnormal physical exam findings must be documented and will be followed by a physician or other qualified staff at the next scheduled visit.

Table 1. Procedures by Day**OVERVIEW**

| Days -30 to Day 0 (approx.) | Day 0 Baseline buprenorphine PK | | |
|---|---|--|--|
| Screening and assessment at CARI/Motivate facility including phenotyping battery (PhAB) | Outpatient visit to CRU for baseline buprenorphine PK measurement | | |
| | PK/Safety Testing Week 1, Day 1 | PK/Safety Testing Week 1, Day 2 - Day 3 | PK /Safety Testing Week 1, Day 4-7 |
| | Admit to CRU for overnight stay, urine drug screen, vital signs, physical examination, COWS | Lemborexant 5mg or placebo plus Buprenorphine-naloxone safety including pulse oximetry, agitation and sedation, PK, pupillometry, withdrawal, impulsivity measures, and subjective effects. | Follow-up at CARI/MOTIVATE for withdrawal, impulsivity measures, subjective effects, and side effects. |
| | PK/Safety Testing Week 2, Day 1 | PK/Safety Testing Week 2, Day 2 - Day 3 | PK/Safety Testing Week 2, Day 4-7 |
| | Admit to CRU, urine drug screen, vital signs, physical examination, COWS. Also stay overnight for safety and observation. | Lemborexant 10mg or placebo plus Buprenorphine-naloxone safety including pulse oximetry, agitation and sedation, PK, pupillometry, withdrawal, impulsivity measures, and subjective effects. | Follow-up at CARI/MOTIVATE for withdrawal, impulsivity measures, subjective effects, and side effects. |

Schedule of Procedures and Assessments:

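### Buprenorphine stability is described but not required or defined at entry, and the PK contrast with Day 0 allows for neither dose changes nor carry-over from the preceding dose

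*Combined protocol and SAP*

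**What the plan says.** **Entry.** Inclusion criterion 3 requires a person "currently engaged in buprenorphine-naloxone treatment at a sublingual film daily dose ranging from 8mg/2mg to 24mg/6mg" (or within a tablet range). Criterion 4 adds a urine check: "Have a positive urine drug screen for buprenorphine during screening and on admission to the clinical research unit to document buprenorphine use". That shows use, but not dose, duration or timing.

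**Description of the sample.** The Background section states: "All participants will be currently stable in MAT treatment with buprenorphine and have symptoms of insomnia". The brief description of the protocol refers to participants "that have been stabilized on buprenorphine-naloxone sublingual film daily dose ranging from 8mg/2mg to 24mg/6mg". Neither term is defined and neither appears among the criteria.

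**Dose during the study.** Dosage/Dosage Regimen states that "all subjects will receive a dose equivalent to their current prescribed dose of buprenorphine-naloxone sublingually as a film or tablet". Concurrent Medications states: "All participants should be maintained on the same medications throughout the entire study period, as medically feasible, with no introduction of new chronic therapies". Formulation of Test Product states: "Buprenorphine HCl/naloxone films will be used for this study, in unblinded fashion", which does not match the film-or-tablet wording.

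**Timing.** Table 1 makes Day 0 an outpatient visit, while each lemborexant session follows a night on the unit. Table 2 marks study buprenorphine on Day 0 and Day 2 only. Table 3 times the session dose at 8:05. For other medication, the Concomitant Medications paragraph says: "Dose, route, unit frequency of administration, and indication for administration and dates of medication will be captured". Clock time is not listed.

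**Analysis.** Statistical Methods derives Cmax, Tmax, AUC, half-life, CL/F and metabolite ratios, and compares them within subjects. Hypothesis 1, however, is stated against placebo.

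**The concern.** Buprenorphine PK is a primary outcome, and each lemborexant participant's reference is his or her own Day 0 profile. That reference works only if exposure would otherwise be the same on Day 0 and at the later sessions. Three things can break this without any interaction:

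- The participant has not reached steady state on Day 0.
- The prescribed dose or product differs at a later session.
- The interval since the preceding dose differs between sessions.

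The order is fixed as Day 0, then 5 mg, then 10 mg. Continuing accumulation or upward titration therefore raises the later sessions, the 10 mg session most. It could look like an interaction or mask one in the opposite direction.

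**Working it through.** The plan gives no figure on this point: no half-life, variance or equivalence margin. What follows illustrates size only.

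**Inputs from the documents.** Buprenorphine is given at 8:05 and sampled to 4:00 pm, a window of 7.92 h. If Week 1 starts the day after Day 0 and the weeks run on, the sessions fall 2 and 9 days after Day 0. There are 12 lemborexant and 6 placebo participants.

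**Assumptions, not in the documents.** One compartment, linear kinetics, a dose every 24 h, half-life 24–42 h, absorption rate 1.5/h.

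**1. Recent start.** Let A0 be the area in the window from the session's own dose, A24 the area from a dose 24 h earlier, and r = 2^(−24/half-life). With n earlier daily doses:

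AUC(n) = A0 + A24 × (1 − rⁿ)/(1 − r)

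For a start three days before Day 0, n is 3 on Day 0, 5 two days later and 12 nine days later.

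| Half-life | r | A0 | A24 | AUC(3) | AUC(5) | AUC(12) | Ratio, +2 days | Ratio, +9 days |
|---|---|---|---|---|---|---|---|---|
| 24 h | 0.500 | 6.536 | 3.608 | 12.850 | 13.526 | 13.750 | 1.05 | 1.07 |
| 42 h | 0.673 | 6.830 | 5.050 | 17.565 | 20.139 | 22.137 | 1.15 | 1.26 |

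Study Drug and Dosage defines AUC to infinity. On that scale the ratio is approximately (1 − r^(n+d+1))/(1 − r^(n+1)), with d the days since Day 0. This gives 1.05–1.14 and 1.07–1.25, so the choice of AUC changes little.

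A start one day before Day 0 gives 1.27–1.48 and 1.36–1.85. A start seven days before gives at most 1.025 and 1.044.

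**2. Effect on the group.** One three-day starter among 12, at the worst ratio, gives 1.26^(1/12) = 1.02. Three give 1.26^(3/12) = 1.06.

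**3. Dose change.** Going from 16 to 24 mg, both within the film range, multiplies steady-state Cmax and AUC by 24/16 = 1.5. One such case in 12 gives 1.5^(1/12) = 1.03, and three give 1.5^(3/12) = 1.11. The counts are illustrative.

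Dividing by dose corrects this only at steady state. On the first day of a 1.5-fold increase (half-life 24 h, absorption 1/h, 8 h window) AUC rises 1.23-fold, so dose normalisation alone would give 1.23/1.5 = 0.82.

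**4. Prior-dose interval.** At steady state, a preceding dose 24 h rather than 14 h earlier lowers AUC by 11–15% and the pre-dose level by 15–25%.

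**5. Can it be corrected?** In this model, subtracting the decaying pre-dose level from the profile returns the ratio in step 1 to 1.00 at every half-life tried. The samples exist: 8:00 on Day 0, and 7:00 and 8:00 on Day 2. Lemborexant is given at 7:05 on Day 2, so the 8:00 sample follows it by 55 minutes and only the 7:00 sample precedes treatment. The hour's difference from Day 0 is worth 2–3% at these half-lives (2^(−1/24) = 0.97, 2^(−1/42) = 0.98).

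**The case against.** The other side has real force, and several stronger readings should be set aside.

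- **A reader might infer that any newly prescribed dose simply carries into a session.** The documents do not go that far. Concurrent Medications asks for constant medication as far as medically feasible, and the word current in the dosing text could mean the dose at entry. What stands is that the two passages do not settle which is meant.
- **A reader might infer that drift would inevitably be taken for an interaction.** The randomised placebo group follows the same Day 0, Week 1 and Week 2 schedule, so drift common to both arms would show in both. What stands is that the PK analysis text does not use that group.
- **A reader might infer that the problem is beyond repair once data are collected.** The pre-dose samples contradict this, as step 5 shows. The plan simply does not provide for such an adjustment.
- **The largest ratios need an extreme case.** Ratios up to 1.85 require someone who started one day before Day 0, already within the dose range, with screening completed and in a sample described as stable. They should not be taken as typical.
- **CL/F is listed and allows for a known dose.** This is correct, but it does not allow for incomplete accumulation or an unknown prior-dose interval.
- **Interval differences may be only noise.** With habitual once-daily dosing, no directional shift is shown. The move from an outpatient Day 0 to an overnight stay makes one possible, but the documents do not establish it.

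**Conclusion.** The point holds as a gap in both specification and analysis. Criterion 3 does not carry the stability that the design text assumes, and the session dose is not expressly the Day 0 dose. The preceding dose is not timed, and Cmax and AUC enter a within-subject comparison without any correction.

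Following the plan as written can therefore shift a primary PK contrast with no interaction present. Under half-lives of 24–42 h, a start three days before Day 0 gives individual AUC ratios of 1.05–1.15 and 1.07–1.26. The group effect is about 2% or less for one such participant in 12 and becomes material only if several are affected. The documents do not show how many would be. The direction of the accumulation effect is firm; its size depends on the assumed half-life and linear kinetics.

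This should be put right before the PK analysis is fixed. It does not show that the PK comparison will be invalid.

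**What to change.** 1. **Entry.** Reconcile criterion 3 with the Background and the brief description by placing the stability requirement in the criterion. The sponsor should define and justify the period on an unchanged dose and product.
2. **Session dose.** Reconcile Dosage/Dosage Regimen with Concurrent Medications on whether the session dose is the Day 0 dose, and with Formulation of Test Product on film or tablet. Record the dose and product given at each session and dose-normalise Cmax and AUC. The criterion's film and tablet ranges differ by 8/5.7 = 24/17.1 = 1.40, so normalising by nominal milligrams is meaningful only within one product. Keep all sessions in the main analysis. A dose change after randomisation may be related to treatment, so excluding changed-dose sessions belongs in a sensitivity analysis only.
3. **Carry-over.** Record the clock time of the last buprenorphine dose before Day 0 and before each Day 2. Pre-specify adjustment for that interval or for the pre-dose level, using the 8:00 sample on Day 0 and the 7:00 pre-lemborexant sample on Day 2. If the residual is subtracted, do so before dividing by dose.
4. **Placebo.** Add a placebo-adjusted change from Day 0, in line with hypothesis 1, and report it beside the within-subject contrast.

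Repeating Day 0 after a dose change is not a ready alternative: the note to Table 2 allows repeats only where procedures could not be completed.

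**Cost.** One eligibility phrase, one CRF field and a few analysis sentences. Some recently started patients may wait within the screening window of about 30 days. The placebo-adjusted contrast is less precise: with equal variances its standard error is √(1/12 + 1/6)/√(1/12) = 1.73 times that of the within-group contrast. No change to any patient's treatment is proposed.
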